Appendix VI: CTCAE Criteria

Neurotoxicity Evaluation

Grade	I	II	III	IV
NCI-CTCAE v5.0	Asymptomatic	Moderate symptoms; limiting instrumental ADL	Severe symptoms; limiting self-care ADL	Life-threatening consequences; urgent intervention indicated
Questions	Sample answers for each toxicity grade			
Do you have problems tying your shoe laces, buttoning your shirts, fastening buckles or pulling up zippers?	“No, I might feel some tingling in my hands, but I have no problems tying laces, buttoning shirts, fastening buckles or pulling up zippers”	“It is a bit harder than before, but I can still tie laces, button shirts, fasten buckles or pull up zippers”	“I have severe difficulties tying shoe laces, buttoning shirts, fastening buckles or pulling up zippers” or “I cannot tie laces, button shirts, fasten buckles or pull up zippers anymore”	“I haven’t been able to tie laces, button shirts, fasten buckles or pull up zippers for weeks”
Do you have problems writing?	“No, I might feel some tingling in my hands, but I have no problems writing”	“It is a bit harder than before, but I can still write”	“I have severe difficulties writing” or “I cannot write anymore”	“I haven’t been able to write for weeks”
Do you have problems putting on your jewelry or your watch?	“No, I might feel some tingling in my hands, but I have no problems putting on my jewelry or my watch”	“It is a bit harder than before, but I can still put on my jewelry or my watch”	“I have severe difficulties putting on my jewelry or my watch” or “I cannot put on my jewelry or my watch anymore”	“I haven’t been able to put on my jewelry or my watch for weeks”
Do you have problems walking?	“No, I might feel some tingling in my feet, but I have no problems walking”	“It is a bit harder than before, but I can still walk”	“I have severe difficulties walking” or “I cannot walk anymore”	“I haven’t been able to walk for weeks”

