3.0 Registration Patient Eligibility

3.1 Registration - Inclusion Criteria

- 3.11 Age \geq 18 years
- 3.12 English speaking
- 3.13 Cancer diagnosis of any tumor type with chemotherapy-induced neuropathy
- 3.14 At least 4 out of 10 severity of neuropathy pain and/or tingling per appendix IV
- 3.15 Stable for at least 7 days prior to registration on medications for neuropathy, if any are being used
- 3.16 ECOG Performance Status (PS) 0, 1 or 2 (Appendix VIII).
- 3.17 **Negative pregnancy test done \leq 7 days prior to registration, for persons of childbearing potential only.**

NOTE: If a urine test is positive or cannot be confirmed as negative, a serum pregnancy test will be required.

- 3.18 Able to provide written informed consent
- 3.19a Ability to complete questionnaire(s) by themselves or with assistance.
- 3.19b No evidence of residual cancer
- 3.19c Required Initial Laboratory Values: Following completion of chemotherapy, patients must have had a CBC and serum chemistries, including the following:
 - Platelet count $>$ 100,000/mm³
 - Absolute neutrophil count (ANC) \geq 1,000/mm³
 - Hemoglobin $>$ 11 g/dL
 - Serum transaminase [ALT or AST] \leq 1.2 x upper limit of normal (ULN)
 - Alkaline phosphatase \leq 1.2 x ULN
 - Serum creatinine \leq 1.2 x ULN

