16.2 Analysis Plan for Secondary Outcome and Translational Endpoint

Analyses for secondary endpoints will also be descriptive in nature. Due to the exploratory nature of this research, we will not adjust for multiple comparisons for the secondary analyses. Analyses of the motor and autonomic subscales will be identical to the analyses of the primary endpoint. Analyses of CTCAE grades and the symptom questionnaire individual items will compare the incidence and maximum (worst) values between arms. Fisher's exact tests will be used to compare incidence rates and Wilcoxon rank-sum tests will be used to compare maximum values between arms.

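### Appendix VI separates Grade IV (life-threatening) neuropathy from Grade III by duration alone, so a stable inability can be recorded as life-threatening

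*Combined protocol and SAP*

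**What the plan says.** Appendix VI sets four questions (fastening clothes and shoes, writing, jewelry or watch, walking) against Grades I to IV, with a header definition and example replies for each grade. For writing, the Grade III replies include "I cannot write anymore". The Grade IV reply is that the patient has not "been able to write for weeks". The other three questions follow the same pattern. The Grade IV header is "Life-threatening consequences; urgent intervention indicated". The replies as a whole are labelled "Sample answers for each toxicity grade".

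Sections 2.2 and 16.1 name the CTCAE neuropathy scale as a secondary endpoint. Section 4.1 schedules it at baseline and at the end of weeks 1, 2, 3 and 4. Footnote f of that table has a research nurse or clinician complete it by call, using Appendix VI. Section 10.6 repeats the requirement for baseline and each evaluation.

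Section 16.2 analyses CTCAE grades by incidence (Fisher's exact test) and by "maximum (worst) values between arms" (Wilcoxon rank-sum test). It gives the baseline grade no role and does not say whether the worst grade is taken within each two-week period or over the whole study.

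Grade I is headed "Asymptomatic", but its writing reply is "I might feel some tingling in my hands, but I have no problems writing". Criterion 3.14 admits only patients with "At least 4 out of 10 severity of neuropathy pain and/or tingling per appendix IV".

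**The concern.** A grading key should let two raters who hear the same reply record the same grade. Here the header and the example reply for Grade IV point to different grades, and nothing says which one governs. A rater who follows the replies records Grade IV for someone who has been unable to write for some time. A rater who follows the header would not.

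Two things are at stake. First, tabulated Grade IV neuropathy would suggest life-threatening events that did not happen. Second, the step from III to IV carries duration, not severity. The top of the scale therefore says little about whether the cream helped, and a worst-grade comparison would partly reflect how long patients had been disabled before they enrolled.

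**Working it through.** **1. The plan's own figure.** The plan gives no figure for this endpoint. Its only design calculation is the power table in Section 16.1, for the primary endpoint. A noncentral-t calculation with 20 per arm and two-sided alpha 0.05 gives 0.338, 0.456, 0.578, 0.693, 0.792 and 0.869 for effect sizes 0.5 to 1.0. The table prints 0.34, 0.46, 0.58, 0.69, 0.79 and 0.87. It is reproduced and plays no part in this point.

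**2. Header against reply.**

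| | Header | Writing reply | What the reply adds |
|---|---|---|---|
| Grade III | severe, limits self-care | severe difficulty, or total loss | no duration given |
| Grade IV | life-threatening, urgent | total loss, lasting weeks | duration only |

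None of the four Grade IV replies mentions danger to life or an urgent intervention. The contradiction lies within one page and needs no outside source.

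**3. What the replies do to an unchanging patient.** Let the inability be total and constant, starting D weeks before baseline. Let W be the number of weeks a rater treats as enough for the Grade IV reply. The documents do not define it, so W = 2, 3 and 4 are assumptions. At week t (0 to 4) the grade is IV if D + t ≥ W, otherwise III.

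| W | D | Grades at weeks 0, 1, 2, 3, 4 | Worst, weeks 1–2 | Worst, weeks 3–4 |
|---|---|---|---|---|
| 2 | 0 | 3, 3, 4, 4, 4 | 4 | 4 |
| 2 | 1 | 3, 4, 4, 4, 4 | 4 | 4 |
| 3 | 0 | 3, 3, 3, 4, 4 | 3 | 4 |
| 3 | 1 | 3, 3, 4, 4, 4 | 4 | 4 |
| 3 | 2 | 3, 4, 4, 4, 4 | 4 | 4 |
| 4 | 0 | 3, 3, 3, 3, 4 | 3 | 4 |
| 4 | 1 | 3, 3, 3, 4, 4 | 3 | 4 |
| 4 | 2 | 3, 3, 4, 4, 4 | 4 | 4 |
| 4 | 3 | 3, 4, 4, 4, 4 | 4 | 4 |
| any | 4 or more | 4, 4, 4, 4, 4 | 4 | 4 |

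The grade drifts only when D < W. The worst grade differs between the two periods in three rows: W = 3 with D = 0, and W = 4 with D = 0 or 1. Week 0 is taken as Day 1. Section 4.1 lets the baseline visit fall up to 30 days earlier, which would widen the room for drift by up to 30/7 = 4.3 weeks.

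**4. Which row patients fall in.** Exclusion 3.25 removes anyone given chemotherapy in the previous 3 months. A fixed inability caused by that chemotherapy would usually have D of 12 weeks or so, or more. That is the last row: Grade IV at baseline and at every later call.

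**5. Number affected.** The documents give no share of patients who would report total, long-standing inability. As an assumed range, 0.05 × 40 = 2 and 0.20 × 40 = 8.

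**6. Worst grade against change from baseline.** Take three hypothetical patients, graded at baseline, week 1 and week 2:

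- 4, 4, 4: worst on treatment 4, change at week 2 = 4 − 4 = 0.
- 4, 4, 2: worst 4, change = 2 − 4 = −2.
- 2, 4, 4: worst 4, change = 4 − 2 = +2.

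The worst grade cannot tell them apart. Since every patient enters with neuropathy, the entry state strongly influences that summary.

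**The case against.** The strongest reply has five parts.

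- **The replies are only examples.** They are labelled as samples, and Sections 10.1 and 10.6 tie grading to CTCAE v5.0, so a rater could follow the header. This stands as far as it goes. The gap is that no precedence rule is stated, while Section 4.1 directs the caller to use Appendix VI.
- **Few patients are exposed.** Criterion 3.16 requires ECOG 0 to 2, and Appendix VIII describes grade 2 as walking and managing self-care. Total inability to walk or dress fits poorly with that, which leaves mainly writing and jewelry. This stands and is a reason to give a range, not a single count.
- **Randomisation balances time.** A reader might infer that the grade drifts upward during the study and so counts against whichever cream comes second. The documents do not support that. Most fixed inabilities would already be Grade IV at entry, time passes equally in both randomised arms, and Section 16.2 compares incidence and worst values, not worsening. A within-patient comparison across periods would be more exposed, but only in the three rows noted above.
- **The safety consequence is limited.** Section 10.1 separates severe from serious. Section 10.4 does list a life-threatening event as serious, but its table gives Grades 3 to 5 one timeframe, and the threshold in Section 16.32 is passed by Grades III and IV alike. The harm is a false label, visible from the baseline grade.
- **It is a descriptive secondary endpoint in a pilot.** This is true and limits the weight of the point. But Section 16.1 says the pilot's estimates are to inform a phase III design.

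A reader might also take the tingling reply under the Grade I header as part of the same fault. It is a separate labelling mismatch. It cannot make a grade change with time, and relabelling the column would change no score.

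**Conclusion.** The point holds. The Grade III and Grade IV columns of Appendix VI differ only in duration, the Grade IV replies do not meet the Grade IV header, and no rule resolves the conflict. The usual result would be a false Grade IV from baseline and a ceiling. Drift from III to IV is possible but needs an inability of recent onset, or a patient who words the answer differently at a later call.

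Between randomised arms the effect is mainly misclassification and lost sensitivity. The CIPN20 sensory endpoint and its power table are unaffected. The range of 2 to 8 of 40 rests wholly on the assumed 5% to 20%, and no single figure can be drawn from the documents. The time courses rest on assumed values for an undefined duration. Whether the printed headers match the published CTCAE v5.0 was not checked, since that source is outside the documents.

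**What to change.** 1. In Appendix VI, move the four weeks-long replies into the Grade III column, state that the printed definition prevails over the sample replies, and reserve Grade IV for events that meet its definition. This means re-issuing a one-page call form.
2. In Section 16.2, compare change from the baseline grade between arms, and not only the raw worst grade. The grade at the end of week 2 minus the baseline grade would match the timing of the primary endpoint. No new data are needed, because Sections 4.1 and 10.6 already require the baseline grade. A sentence should make clear that Section 10.61, which waives grading of pretreatment symptoms, does not apply to this scale. Make this change together with the first: with the key as it stands, a change score would count any drift from III to IV as worsening.
3. Record the reply to each of the four questions and state how they combine into one grade, which the documents do not say. Once total loss and severe difficulty share Grade III, a move between them shows only at item level.
4. If calls have begun, re-map IV to III only where the grade rests on a weeks-long reply and the item-level answer was recorded. Leave any event that meets the printed Grade IV definition as it is.

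If the Grade I label is tidied in the same re-issue, treat that as an editorial change.

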Appendix VII: PRODUCT AND PLACEBO INFORMATION

- I. Source of Hemp: The source of the Hemp is USA grown from pesticide-free farms.
Manufacturer: Nightingale Remedies, Portland OR
- II. Method of CBD extraction: CBD isolate is extracted using Super Critical C02 Extraction method. This process is described below:

An extractor chamber is filled with ground cannabis/hemp material (called trim). A pump forces pressurized carbon dioxide gas at the optimum temperature (ScCO2) into the extractor chamber. The supercritical carbon dioxide interacts with the cannabis, dissolving the cannabinoid compounds it contains. The supercritical CO2 carries the cannabis oil particles past a pressure release valve to a cyclonic separator. In the separator, the pressure is lower and the carbon dioxide and cannabis oil separates. The carbon dioxide rises and is routed back to the CO2 tank for reuse in the case of a closed loop system. The cannabis oil, waxes and resins descend in the separator where they are captured by a collection vessel. The resulting substance is processed further into various products, such as CBD-rich “cannabis oil”, free of any solvents.
- III. Manufacturing Process: The manufacturing process is in a certified facility (see attachments). All ingredients are pre-screened with COA's for each ingredient. Production standards of cGMP are followed in every step of the process. The manufacturing process is a controlled environment and FDA / cGMP certified.
- IV. Ingredients

Placebo:
Water, Organic Coconut Oil, Grapeseed Oil, Emulsifying Wax, Stearic Acid, Glycerin, Xanthan Gum, Phenoxyethanol, Tetrasodium Glutamate Diacetate, isopropyl palmitate, caprylic/capric triglyceride, propylene glycol, ceteareth-20, cetearyl alcohol, glyceryl stearate, PEG-100 stearate, dimethicone, octyldodecanol, hydroxyethyl acrylate/sodium acryloyldimethyl taurate copolymer, lecithin, phenoxyethanol, ethylhexylglycerin, trolamine.

Experimental Cream:
Water, CBD Isolate* (Hemp Extract), Organic Coconut Oil, Grapeseed Oil, Emulsifying Wax, Stearic Acid, Glycerin, Xanthan Gum, Phenoxyethanol, Tetrasodium Glutamate Diacetate, isopropyl palmitate, caprylic/capric triglyceride, propylene glycol, ceteareth-20, cetearyl alcohol, glyceryl stearate, PEG-100 stearate, dimethicone, octyldodecanol, hydroxyethyl acrylate/sodium acryloyldimethyl taurate copolymer, lecithin, phenoxyethanol, ethylhexylglycerin, trolamine.

***Active Product: Added CBD isolate to placebo base, 250 mg per 1.7 oz**
- V. Certificate of Analysis: COA showing full panel test results is included in the current Investigator's brochure. The COA shows that there is 0% THC in the final CBD Isolate product.
- VI. Study Product: The study product is being manufactured specifically for this study. It contains the ingredients listed above and will not have the herbals that are contained in the

marketed Nightingale Remedies product “CBD Relief Cream”. COA for the study product is included in the current Investigator’s Brochure.

Appendix VIII ECOG Performance Status

ECOG PERFORMANCE STATUS*

Grade	ECOG
0	Fully active, able to carry on all pre-disease performance without restriction
1	Restricted in physically strenuous activity but ambulatory and able to carry out work of a light or sedentary nature, e.g., light house work, office work
2	Ambulatory and capable of all selfcare but unable to carry out any work activities. Up and about more than 50% of waking hours
3	Capable of only limited selfcare, confined to bed or chair more than 50% of waking hours.
4	Completely disabled. Cannot carry on any selfcare. Totally confined to bed or chair.
5	Dead

*As published in Am. J. Clin. Oncol.:

The ECOG Performance Status is in the public domain therefore available for public use. To duplicate the scale, please cite the reference above and credit the Eastern Cooperative Oncology Group, Robert Comis M.D., Group Chair.

Appendix IX: Patient Suicidal Thoughts Assessment and Evaluation for Skin Toxicity

Nurse/clinician Phone Call Questions to address regarding suicidal thoughts and potential skin toxicity.

Patients will be asked at the end of each week.

1. Given an abundance of precaution, we want to ask you about whether you have had any thoughts of suicide since starting this protocol?
 - If the answer is 'no', please record.
 - If the answer is 'yes', please record then physician contact is required, and appropriate intervention is to be provided.
2. Do you have skin irritation on your hands and/or feet in the location of the cream application?
3. Do you have any rash, blisters, or open areas of skin in the location of the cream application?
 - Please record responses.
 - If the answer is 'yes' to any of the above two questions, the patient will be asked to come in to be seen by a provider for a skin examination.

Additionally:

4. At the end of weeks 2 and 4, please remind patients to mail in or bring in their questionnaires from the prior 2 weeks.
5. Please note any other pertinent information that the patient provides.

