4.0 Test Schedule

4.1 Test schedule for Chemotherapy-Induced Peripheral Neuropathy

Study Visit	1	2	3	4	5	6	7
Study Time Point	Screening /Baseline (Day -30 to Day 1)	Day 1	End of Week 1	End of Week 2 ^c (+3 Days)	End of Week 3	End of Week 4	End of study
CLINICAL ASSESSMENTS							
Informed consent	X						
Inclusion/exclusion criteria	X ^g						
Demographics/ Medical history	X						
Pregnancy testing ^a	X						
Randomization	X						
Dispense Study Product/Placebo		X		X			
Collect questionnaires							X
Adverse event assessment ^b			X	X	X	X	
STUDY TESTING							
EORTC QLQ-CIPN 20 instrument (Appendix I)	X		X	X	X	X	
Global impression of change (Appendix II)			X	X	X	X	
Chemotherapy Induced Peripheral Neuropathy Assessment Tool (Appendix III)	X		X	X	X	X	
Symptom experience diary (Appendix Va & Vb)	X ^d		X ^e	X ^e	X ^e	X ^e	
NCI-CTCAE neuropathy scale ^f (Appendix VI)	X		X	X	X	X	
Cycle = 14 days							
^a For individuals of childbearing potential. Must be done \leq 7 days prior to registration.							
^b Research nurse or clinician to call patient. Including inquiry about skin toxicity and to assess for suicidal thoughts (Appendix IX). Ask the patient if they have missed any doses of the study							

medication and provide education if necessary. Note any other pertinent information that the patient provides.

^c After subject completes week 2 they will turn in completed questionnaire diary and start the next supply of cream within 1-3 days after completing the first 2 weeks, ideally.

^d Appendix Va: System Experience Diary used for baseline assessment. Must be completed prior to application of study medication.

^e Appendix Vb: System Experience Diary used for weekly assessments. Must be completed at the end of each week.

^f To be completed during research nurse or clinician call to patient per Appendix VI.

^g Required Initial Laboratory Values per inclusion criteria 3.19c can be done any time after the patient has completed their chemotherapy and prior to study registration.

5.0 Stratification Factors:

- Gender (Male, Female, or Other)

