15.12 Nursing guidelines

Educate patient regarding this protocol and address questions.

1. Instruct patients to report any rash or burning with application
2. Instruct patients to avoid eye contact after applying lotion
3. Agent should be stored at room temperature

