Appendix Vb: Symptom Experience Diary —During Treatment

Please circle **ONE** number for each item that best describes you over the past 7 days.

1. Over the past week, please rate your quality of life:

2. Do you have any skin rash on your hands or feet:

3. How many doses of the study medication do you think that you missed over the past week?
(Circle one answer)

0 times 1-2 times 3-4 times More than 5 times

4. Did you have any skin side effects from the study product?

No

Yes, if so, please describe the symptom(s) and severity:

5. Did you have any other side effects from the study product?

No

Yes, if so, please describe the symptom(s) and severity:

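### Appendix IX asks about suicidal thoughts cumulatively and never at baseline, so an early yes hides second-cream status; its present-tense skin items can leave transient reactions out of the adverse event record

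*Combined protocol and SAP*

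**What the plan says.** Appendix IX is the telephone script for two risks the protocol chose to ask about actively. On timing it states: "Patients will be asked at the end of each week".

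- **Item 1** asks: "we want to ask you about whether you have had any thoughts of suicide since starting this protocol". For a yes, the caller is told: "please record then physician contact is required, and appropriate intervention is to be provided".
- **Items 2 and 3** ask: "Do you have skin irritation on your hands and/or feet in the location of the cream application" and "Do you have any rash, blisters, or open areas of skin in the location of the cream application". A yes to either brings the patient in for a skin examination.
- **Schedule (Section 4.1).** Appendix IX enters through footnote b to the adverse event row. That row is marked at the end of weeks 1, 2, 3 and 4, with no mark at Screening/Baseline or Day 1. Screening can open 30 days before Day 1.
- **Treatment (Sections 2.0 and 7.1).** Each cream is used for 14 days, the switch comes after week 2, and there is no washout.
- **Diary (Appendices Va and Vb).** The visible baseline items are quality of life and rash. The weekly form has patients answer "for each item that best describes you over the past 7 days", and covers rash, skin side effects and other side effects.
- **Recording and analysis.** Section 10.62 covers other adverse events at the weekly calls and excludes the questionnaire booklets as a source for adverse event documentation. Section 16.2 compares incidence and worst values of CTCAE grades and diary items between arms, without naming the period.

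**The concern.** Section 2.1 makes side effects of the CBD cream against placebo one of the trial's two aims. In a cross-over, a safety answer helps with that aim only if it can be tied to the cream in use.

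Item 1 keeps one fixed starting point while the cream changes under it, so an old, resolved episode and a new one on the second cream give the same answer. Without a baseline asking, a yes at the first call cannot be read as new. Items 2 and 3 have the opposite limitation: they describe the moment of the call and not the week before it. What is at stake is recurrence or resolution of suicidal thoughts on the second cream, and completeness of the skin entries in the adverse event record.

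**Working it through.** The plan gives no figure on this point to reproduce. The check is an enumeration, followed by a comparison of sections.

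**Inputs.** Four weekly calls (Section 4.1; Appendix IX). Weeks 1-2 are on the first cream and weeks 3-4 on the second (Section 7.1). Recall is assumed accurate.

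**Step 1: what item 1 can show.** Each week either has suicidal thoughts or does not, giving 2^4 = 16 histories. A cumulative question returns yes at call *k* if any week from 1 to *k* was positive. The 16 histories then produce five answer patterns (N = no, Y = yes):

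| Answers, calls 1-4 | Histories | First cream only | Second cream only | Both creams | Neither |
|---|---|---|---|---|---|
| N N N N | 1 | 0 | 0 | 0 | 1 |
| N N N Y | 1 | 0 | 1 | 0 | 0 |
| N N Y Y | 2 | 0 | 2 | 0 | 0 |
| N Y Y Y | 4 | 1 | 0 | 3 | 0 |
| Y Y Y Y | 8 | 2 | 0 | 6 | 0 |

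- The first yes always falls in an identifiable cream period. At call 1 or 2 it belongs to the first period, and at call 3 or 4 it follows recorded no answers and belongs to the second.
- In the last two rows, first-cream-only and both-creams share the same answers. These rows hold 4 + 8 = 12 of the 16 histories: 1 + 2 = 3 first-cream-only and 3 + 6 = 9 both-creams. This counts histories and says nothing about how likely each is.
- The four period-level states therefore collapse to three.

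**Step 2: the same item with a since-last-call window.** Call *k* now returns the status of week *k*, so the answers are the history itself and all four states are distinguishable. Section 4.1 (footnote c) allows 1-3 days between creams, so a yes at call 3 could fall in that gap. An onset date settles this.

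**Step 3: baseline.** The row carrying Appendix IX has no baseline mark. The visible items of Appendix Va do not include suicidality. Section 6.4 requires baseline symptoms by reference to Section 10.6, which names only the neurotoxicity evaluation, and Section 10.61 says pretreatment conditions need not be graded. Because screening may start up to 30 days before Day 1, the window in item 1 can also include days before any cream. Thoughts continuing from before the first application give the same yes at call 1 as thoughts that began on the first cream.

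**Step 4: a skin reaction that starts and clears between calls.**

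| Source | Looks back? | Captures it? | Use |
|---|---|---|---|
| Appendix IX items 2-3 | No | No, on a literal answer | Answers recorded at the call |
| Appendix Vb diary | Yes, 7 days | Yes | Questionnaire comparison (Section 16.2), not adverse event documentation (Section 10.62) |
| Other adverse event inquiry at the call | Not scripted | Possibly | Adverse event record |

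Such a reaction can therefore appear in the questionnaire analysis and be absent from the adverse event record.

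**The case against.** The strongest reply is that the protocol has more safeguards than the script alone suggests.

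- Two recorded calls fall in each cream period, so a first yes is placed on a cream. **This stands.** A reader might infer that events in general cannot be attributed to a cream, and the documents do not support that.
- No section tabulates item 1 answers by cream or forms a within-patient contrast from them. **This stands.** A reader might infer that an early episode counts equally under both creams and cancels out, but that presumes an analysis the plan does not describe. For a first-period comparison, a cumulative window does little harm.
- Randomization protects the first-period comparison from pre-existing thoughts. **This stands on average.** It does not help in reading an individual patient's yes.
- The diary has a 7-day window, a baseline rash item and a place in the between-arm analysis. **This stands for the questionnaire comparison.** Section 10.62 prevents it from closing the gap in the adverse event record.
- Burning on application has no scripted question, but Section 15.12 says: "Instruct patients to report any rash or burning with application". The weekly call also covers other adverse events. **This stands**, so a separate burning or pain item is not pressed here.
- Physician contact after a yes, the caller's free notes, or case report forms that are not shown may supply dates. **This is possible**, but the available text specifies none.

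**Conclusion.** The point holds in a limited form. After a yes by week 2, item 1 cannot distinguish first-cream-only from both-creams, so recurrence or resolution on the second cream is not visible in that item. Thoughts continuing from before treatment cannot be separated from onset on the first cream. Skin reactions that clear between calls can be missed in the adverse event record, although the diary may hold them.

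The size is three distinguishable states in place of four, with 12 of 16 histories affected. This rests on accurate recall, literal answers, and there being no onset-date field or baseline question in material not shown. No miss rate for skin reactions can be given, because the documents state no duration for them.

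This is an inexpensive improvement to safety data capture in a descriptive 40-patient pilot. The primary endpoint is unaffected. Rewording will not resolve carry-over: with no washout, a reaction seen in week 3 may still belong to the first cream.

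**What to change.** Change the Appendix IX script as follows.

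1. **Item 1:** ask about the time since our last call or, at the first call, since you first applied the cream.
2. **Baseline:** ask about suicidal thoughts once before first application and mark this in Section 4.1, so that later answers can be read against it. Any response to a baseline yes is for the sponsor to decide.
3. **Items 2 and 3:** ask whether the problem has occurred since our last call (at the first call, since first application), with a separate tick for present now.
4. **Dates:** record the onset date for any yes, so it can be set against the date of the switch.

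Leave the physician-contact and skin-examination steps as the protocol states them. The cost is one extra baseline question, slightly longer calls and a revised form, with no added visits.
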